5.3.1. Dose Adjustments

If an AE is attributed to only 1 drug (andecaliximab or nivolumab), the investigator's discretion will be used to determine if the drug not attributed to the adverse event will be withheld based on the investigator's assessment of risk-benefit of withholding 1 or both drugs.

5.3.1.1. Andecaliximab

If a subject experiences a Grade 3 toxicity or greater that is felt to be due to study drug andecaliximab, treatment will be postponed until the toxicity is resolved to Grade 0 or 1 (as defined by CTCAE v 4.03) or returns to the subject's baseline value. If the toxicity is resolved to Grade 0 or 1 or returns to the subject's baseline value, the subject may resume andecaliximab at the originally assigned dose level. If the subject experiences a recurrence of the Grade 3 or greater toxicity after restarting andecaliximab, treatment with andecaliximab will be discontinued.

5.3.1.2. Nivolumab

Please refer to the current nivolumab label or SmPC for your respective region for recommended dose modification guidelines and full discontinuation criteria with nivolumab.

5.4. Prior and Concomitant Medications

At Screening, all medication taken up to 30 days prior to the screening visit will be recorded on the eCRF. At each study visit, the site will capture any and all medications taken by the subject since the last visit or during the visit (as applicable). Concomitant medications include prescription and non-prescription medications, pre-infusion medications (eg, anti-emetics), and vitamins and minerals.

In addition, supportive therapies given during the course of the study (eg, blood transfusion, growth factor) will be collected and recorded on the eCRF.

During the course of the clinical trial, study subjects are anticipated to continue the use of prescribed medications identified during the screening procedures, consistent with study inclusion and exclusion criteria.

Non-study anticancer chemotherapy or immunotherapy (approved or investigational) is not permitted during the trial. If administered, the subject may be removed from the trial.

Inhaled steroids and short courses of oral steroids for anti-emesis or as an appetite stimulant are allowed; however, chronic daily treatment with oral corticosteroids (dose of > 10 mg/day prednisone equivalent) are not.

5.4.1. Acceptable Concomitant Medications

All treatments that the investigator considers necessary for a subject's welfare may be administered at the discretion of the investigator in keeping with the community standards of medical care. All concomitant medication will be recorded on the case report form (CRF) including all prescription, over-the-counter (OTC), herbal supplements, and IV medications and fluids. If changes occur during the trial period, documentation of drug dosage, frequency, route, and date may also be included on the CRF.

All concomitant medications received within 30 days before the first dose of trial treatment and 30 days after the last dose of trial treatment should be recorded.

5.4.2. Prohibited Concomitant Medications

Subjects are prohibited from receiving the following therapies during the Screening and Treatment Phase (including retreatment for post-complete response relapse) of this trial:

- Antineoplastic chemotherapy or biological therapy not specified in the protocol
- Immunotherapy not specified in this protocol
- Investigational agents other than those specified by the protocol

- Radiation therapy
 - Note: Radiation therapy to a symptomatic solitary lesion or to the brain may be considered on an exceptional case-by-case basis after consultation with the Sponsor. The subject must have clear measurable disease outside the radiated field. Administration of palliative radiation therapy will be considered clinical progression for the purposes of determining PFS.
- Live vaccines within 30 days prior to the first dose of trial treatment and while participating in the trial. Examples of live vaccines include, but are not limited to, the following: measles, mumps, rubella, chicken pox, yellow fever, rabies, BCG, and typhoid (oral) vaccine. Seasonal influenza vaccines for injection are generally killed virus vaccines and are allowed. However, intranasal influenza vaccines (eg, Flu - Mist®) are live attenuated vaccines, and are not allowed.
- Systemic glucocorticoids for any purpose other than to modulate symptoms from an event of suspected immunologic etiology. The use of physiologic doses of corticosteroids may be approved after consultation with the Sponsor.
 - Note: Inhaled steroids are allowed for management of asthma.

Subjects who, in the assessment by the investigator, require the use of any of the aforementioned treatments for clinical management should be removed from the trial. Subjects may receive other medications that the investigator deems to be medically necessary.

The Exclusion Criteria describes other medications that are prohibited in this trial.

There are no prohibited therapies during the Post-Treatment Follow-up Phase.

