3.6. Premature Discontinuation from Study Treatment

If a subject has discontinued all study treatments prior to definitive disease progression, the subject shall remain on study until at least 1 of the criteria for discontinuation from study is met (Section 3.7). Every attempt should be made to keep the subject in the study and continue to perform tumor evaluation by computed tomography (CT) or magnetic resonance imaging (MRI) every 8 weeks until disease progression. If this is not possible or acceptable to the subject or investigator, the subject may be withdrawn from the study. It is recommended that the investigator consults with the medical monitor prior to removing the subject from study for any reason except subject withdrawal of consent.

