3.7. Discontinuation Criteria from Study

Subject study participation, may be ended due to any of the following reasons:

- Initiation of non-study specific anti-neoplastic therapy in the absence of progression
- Disease progression
- Intercurrent illness that would, in the judgment of the investigator, affect assessments of clinical status to a significant degree
- Withdrawal of consent
- Investigator decision to remove the subject from the study, in consultation with the Gilead Medical Monitor
- Death
- Discontinuation of the study at the request of Gilead, a regulatory agency, or an IRB/IEC
- Lost to follow up

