6.2.9.2. Tumor Imaging

Contrast-enhanced CT (without contrast if use of contrast is contraindicated) or gadolinium-enhanced MRI of the chest, abdomen, and pelvis will be performed at screening, every 8 weeks during the study and at the EOS visit if one has not been performed within the last 8 weeks. CT is the preferred imaging modality for this study. Tumor burden will be evaluated solely based on radiographic imaging per RECIST v 1.1, with the modifications noted in Section 6.2.9.1. Chest x-ray, ultrasound, endoscopy, laparoscopy, positron-emission tomography, radionuclide scans, or tumor markers will not be considered for response assessment.

For radiographic evaluations, it is recommended that the same method of assessment and the same technique (eg, scan type, scanner, subject position, dose of contrast, injection/scan interval) should be used to characterize each identified and reported lesion at baseline and during study treatment and follow-up. Local site study team reading (investigator assessment with site radiology reading) based on RECIST 1.1 will be used to determine subject eligibility.

Scans taken as part of standard medical practice up to 28 days prior to randomization can be used for Screening as long as they are of diagnostic quality and meet all study requirements. During the treatment phase, scans may be performed at time points other than every 8 weeks as clinically indicated to assess tumor progression.

For subjects who stop study treatment in the absence of disease progression (eg, experienced unexpected toxicity), scans should continue to be collected approximately every 8 weeks until disease progression or initiation of systemic anti-tumor therapy other than the study treatment, whichever is earlier.

All relevant clinical and radiographic information required to make each assessment must be made available for source verification and submission to a central reader. CCI [REDACTED] Disease progression will be determined by the investigator or qualified designee.

Imaging should be continued at protocol-specified intervals until whichever of the following occurs first:

- Initial site-assessed disease progression is confirmed
- The start of new anti-cancer treatment
- Withdrawal of consent
- Death
- The end of the study

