6.3. Assessments for Premature Discontinuation from Study

If a subject has discontinued all study treatments prior to definitive disease progression, the subject shall remain on study for follow-up for progression-free survival (see Sections 3.5 and 3.6). Every attempt should be made to keep the subject in the study and continue to perform tumor evaluation by CT or MRI every 8 weeks. Subjects will remain on study until disease progression or initiation of non-study specific anti-neoplastic therapy in the absence of progression, whichever occurs earlier.

If it is not possible to keep the subject on study, or acceptable to the subject or investigator, the subject may be withdrawn. It is recommended that the investigator consults with the medical monitor prior to removing the subject from study for any reason except subject withdrawal of consent.

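### Protocol 5.4.2 directs subjects off the trial for listed therapies that are not anticancer treatment, in conflict with the sections that keep them on study for 8-weekly scans

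*Protocol*

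**What the plan says.** Protocol 5.4.2 covers screening and treatment. It prohibits antineoplastic and immune therapy outside the protocol, other investigational agents, radiation, live vaccines, and systemic glucocorticoids. Glucocorticoids for symptoms of a suspected immunologic event are exempt, and the sponsor may approve physiologic doses. Subjects who, in the investigator's assessment, "require the use of any of the aforementioned treatments for clinical management should be removed from the trial". The sentence covers the whole list and refers to the trial, not to study drug.

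Other sections say who stays on study and for how long:

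- Protocol 3.6 keeps a subject who has stopped all study treatment on study until a criterion in 3.7 is met: "Every attempt should be made to keep the subject in the study and continue to perform tumor evaluation", every 8 weeks until progression.
- Protocol 6.3: "Subjects will remain on study until disease progression or initiation of non-study specific anti-neoplastic therapy in the absence of progression, whichever occurs earlier".
- Protocol 6.2.9.2 lists the events that end imaging. One is "The start of new anti-cancer treatment". Steroids and vaccines are not on the list.
- Protocol 3.7 includes "Initiation of non-study specific anti-neoplastic therapy in the absence of progression". It names neither steroids, vaccines nor investigational agents. Two general routes could apply: investigator decision in consultation with the medical monitor, and intercurrent illness.
- Protocol 5.4 says of non-study anticancer chemotherapy or immunotherapy: "If administered, the subject may be removed from the trial". It also allows short oral steroid courses against nausea and vomiting or to stimulate appetite.

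**The concern.** A site cannot follow 5.4.2 to the letter and also follow 3.6 and 6.3 for a subject who needs a listed therapy that is not anticancer treatment. If 5.4.2 prevails, tumor assessment stops although no event has occurred that the rest of the protocol treats as a reason to stop it.

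The analysis then works with what is left. SAP 6.2.1 censors PFS at the last adequate tumor assessment for a subject who leaves the study without definitive progression or death. SAP 6.1.2 counts a subject without sufficient assessments as a non-responder in the ITT denominator. If the need for non-immunologic steroids follows a worsening condition, censoring at that point is not independent of the outcome. The trial is open-label and the need is judged by the investigator, so the two arms could be affected unequally.

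**Working it through.** **Step 1: go through the 5.4.2 list item by item.**

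- *New anticancer therapy* (antineoplastic, immunotherapy, anticancer investigational agents). Leaving the study is a listed reason in 3.7, 6.3 ends there, and imaging ends there under 6.2.9.2. Protocol 8.3 and SAP 6.2.1 stop PFS follow-up at new therapy, and SAP 6.1 excludes later scans from ORR. No conflict and no added loss.
- *Radiation.* "Administration of palliative radiation therapy will be considered clinical progression for the purposes of determining PFS", and SAP 6.1 and 6.2.1 count radiation as definitive progression. This is a PFS event, not a loss.
- *Systemic glucocorticoids for a suspected immunologic event.* Exempt in 5.4.2. Protocol 3.5.1 also keeps tumor assessments going during dosing interruptions for prolonged steroid tapers. No conflict.
- *Systemic glucocorticoids for other purposes, live vaccines, non-anticancer investigational agents.* Not named in 3.7 and not a reason to stop scans under 3.6, 6.3 or 6.2.9.2, yet 5.4.2 directs removal. **Conflict.**
- *Short oral steroid courses for nausea and vomiting or appetite.* Allowed in 5.4, but inside the 5.4.2 prohibition as written, so a permitted course can trigger removal. **Conflict.** Section 5.4 also makes removal optional, and only for anticancer therapy; 5.4.2 makes it the rule for everything listed.

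**Step 2: reproduce the plan's power.** Inputs from Protocol 3.2 and 8.10: 60 per arm, ORR 25% against 45%, one-sided alpha 10% (z = 1.2816), CMH test, stated power about 83%.

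- Log odds ratio: OR = (0.45 × 0.75)/(0.25 × 0.55) = 2.4545, ln OR = 0.898. SE = √[1/(60 × 0.1875) + 1/(60 × 0.2475)] = 0.395. Power = Φ(0.898/0.395 − 1.2816) = 83.9%.
- Pooled two-proportion formula: Φ[(0.20 − 1.2816 × √(2 × 0.35 × 0.65/60))/√((0.1875 + 0.2475)/60)] = Φ(1.04) = 85.0%.

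The stated figure is reproduced within about 1 point by the odds-ratio form. Step 3 uses the pooled formula, so its results compare with 85.0%.

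**Step 3: illustrate the effect on ORR.** Assumption, not in the documents: a fraction q of an arm is removed under the conflicting items before any response is documented. The arm's ORR becomes p × (1 − q). With 60 per arm, 5% is 3 subjects and 10% is 6.

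| Removed, Arm A / Arm B | ORR A / B | Power |
|---|---|---|
| 0 / 0 | 45% / 25% | 85.0% |
| 5% / 5% | 42.75% / 23.75% | 82.8% |
| 10% / 10% | 40.5% / 22.5% | 80.4% |
| 5% / 0 | 42.75% / 25% | 78.4% |
| 10% / 0 | 40.5% / 25% | 70.4% |

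With no true effect (25% in both arms) and removal in Arm B only, one-sided type I error is about 13% at q = 5% and 17% at q = 10%, instead of 10%.

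Per removed subject, arm ORR falls by 1/60 = 1.7 points only if that subject would have responded and had not yet done so. The expected fall is 0.25 × 1.67 = 0.4 points to 0.45 × 1.67 = 0.75 points.

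**Step 4: PFS.** The documents give neither a removal rate nor a PFS power calculation, so no effect on the hazard ratio can be derived.

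**The case against.** The strongest reply is that 5.4.2 governs screening and treatment, and closes by saying that nothing is prohibited in post-treatment follow-up. On that reading, removal means leaving treatment and entering follow-up, where 3.6, 6.3 and 6.5 keep scans going. This is reasonable, but the sentence says trial and does not separate the two. The ambiguity stands.

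Sections 3.6 and 6.3 are also not absolute. They ask for every attempt and permit withdrawal when staying is not acceptable to the subject or investigator, and 3.7 has its two general routes. These allow case-by-case decisions; 5.4.2 directs removal for the whole list.

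The toxicity-related steroid use most likely to differ between a two-drug and a one-drug arm is exempt, and nothing links live vaccines to worsening disease. That stands, and leaves steroids for non-immunologic, disease-related reasons as the plausible source of informative loss.

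Protocol 8.1.2 takes ORR from best response during treatment, so under that wording scans after treatment would not restore a response. SAP 6.1 is broader: its cut-off is new chemotherapy or radiotherapy, and the note to Table 5 provides for responses after treatment discontinuation. The benefit of further scans to ORR therefore depends on which definition is used.

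A reader might infer that removal for any prohibited therapy damages PFS and response data. Step 1 shows otherwise for anticancer therapy and radiation. A reader might also compute that losing 5% or 10% of one arm's progression events turns a true hazard ratio of 1.0 into about 0.95 or 0.90. That only restates the assumption (1 − 0.05 and 1 − 0.10), with all loss in one arm, just before progression. The documents support neither the rates nor the imbalance.

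**Conclusion.** The conflict is real but narrow. It concerns live vaccines, systemic glucocorticoids for non-immunologic purposes, and non-anticancer investigational agents. Followed literally, 5.4.2 ends scans that the rest of the protocol requires.

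Informative loss is a possible risk of unknown size, not something the documents show. On the assumptions in Step 3, small and equal removal hardly matters (85.0% to 82.8% power at 5% in each arm), while unequal removal could. Responses documented before removal stand, since SAP 6.1 ranks best response across time points. OS is protected by the long-term follow-up in Protocol 3.8. This is a cheap improvement rather than a design flaw. Which therapies should be prohibited, and when study drug should stop, is not judged here.

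**What to change.** Reconcile 5.4.2 with 5.4, 3.6, 3.7 and 6.3, including the two statements on short oral steroid courses. Replace the removal sentence with one that leaves the study-treatment decision to the reconciled rules and states that the subject stays on study under 3.6 and 6.3: scans every 8 weeks until progression or new anticancer therapy, then survival follow-up.

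The cost is one sentence plus the reconciliation. No scan is added beyond those that 3.6 and 6.3 already ask for; the downside is a few more visits for affected subjects. The SAP was written after the primary analysis, so an amendment may come too late for many subjects. SAP 4.1 already tabulates tumor assessment stopped before progression and lists the reasons, so removals under 5.4.2 could be counted by arm from that listing to show whether the issue arose.

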5.5. Accountability for Study Drug

The investigator or designee (eg, pharmacist) is responsible for ensuring adequate accountability of all used and unused investigational medicinal product during the study. This includes acknowledgement of receipt of each shipment of study drug (quantity and condition) and tracking of vials assigned/utilized for subject dosing.

Study drug (andecaliximab and or nivolumab) accountability records will be provided to each study site to:

- Record the date received and quantity of study drug vials
- Record the date, subject number, subject initials, the vial number dispensed
- Record the date, quantity of used and unused vials returned, along with the initials of the person recording the information.

Dispensing records will include the initials of the person dispensing the study drug or supplies.

5.5.1. Study Drug Return or Disposal

The study drugs (andecaliximab and nivolumab) should be disposed of at the site as per local standard operating procedures. Please see pharmacy binder for additional instructions (See Section [9.1.7](#) for details).

6. STUDY PROCEDURES

The study procedures to be conducted for each subject enrolled in the study are presented in tabular form in [Appendix 2](#) and described in the text that follows.

The investigator must document any deviation from protocol procedures and notify the sponsor or contract research organization (CRO).

Safety and tolerability assessments will include regular monitoring of AEs, changes from baseline in laboratory variables, physical examinations, vital signs, and special safety assessments such as ECGs.

From the time of obtaining informed consent through the first administration of study drug, record all SAEs, as well as any non-serious AEs related to protocol-mandated procedures on the AEs eCRF. All other untoward medical occurrences observed during the Screening period, including exacerbation or changes in medical history are to be captured on the medical history eCRF.

6.1. Subject Enrollment and Treatment Assignment

Subject eligibility will be established at the conclusion of the screening evaluations. The screening number and/or subject ID will be assigned for that individual subject by the designated IWRS. Subject eligibility must be determined by results received from the central lab as described in Sections [6.2.2](#) and [6.2.8](#).

It is the responsibility of the investigator to ensure that each subject is eligible for the study before randomization. A subject will be considered enrolled once he or she has completed randomization.

Subjects will undergo procedures defined in [Appendix 2](#). Details regarding randomization and treatment assignment are in Section [5.1](#).

6.2. Study Procedure Descriptions

The following sections describe the individual study procedures outlined in subsequent sections and the schedule of assessments. During the treatment period, all visits may be performed within the windows identified in [Appendix 2](#).

6.2.1. Informed Consent

All subjects must sign and date the most recent IRB/IEC-approved informed consent form before any study specific procedures are performed except where noted in the protocol in relation to standard of care procedures. CCI

6.2.2. Re-Screening Criteria

Subjects who do not randomize within 28 days of screening will be screen failed.

Re-screening may be allowed. Subjects who are re-screened after 28 days must be re-consented with a new screening number and the screening assessments must be repeated. For subjects that are re-screened within 28 days, assessments with results that would exclude the subject will need to be repeated.

Subject eligibility must be determined by results received from the central lab. However, if there has been at least 1 failed attempt to obtain test results from the central lab, eligibility may be determined using local lab results, with documentation of failed attempts, local lab results, and sponsor approval.

6.2.3. Medical & Medication History

A complete medical and surgical history will be obtained by the investigator or designee at screening, including disease history, and recorded on the eCRF.

All medications taken within 30 days prior to screening and during the screening period will be obtained prior to randomization and recorded on the eCRF. At each study visit, the site will capture any and all medications taken by the subject since the last visit or during the visit (as applicable). Concomitant medications include prescription and non-prescription medications, vitamins and minerals.

In addition, supportive therapies given during the course of the study (eg, blood transfusion, growth factor) should be collected and recorded on the eCRF.

6.2.4. Physical Examination

A physical examination (PE) will be performed at screening, end of treatment (EOT), and EOS. This will include assessment of clinical signs and symptoms. The exam will be performed by a physician, a physician's assistant, or nurse practitioner qualified to perform assessments. Breast, genital, and rectal examinations are not required, unless warranted in opinion of the healthcare provider.

A modified physical exam capturing changes from prior exams will be performed on Day 1 and every 4 weeks thereafter, and at the 30-day Safety Follow-up. Height will be collected at Screening only.

